# Table 10. Overview of outcome domains and prioritized hierarchy of outcomes Outcome domain Specific outcome variables

		Primary outcome		
Sport function	1.	KOOS-child 'Sport/play' 0-100 subscale (7 items)		
		Secondary outcomes		
Patient-acceptable Symtom- state	2.	PASS question (Y/N)		
Knee-related Quality of Life	3.	KOOS-child 'Quality of Life' 0-100 subscale (5 items)		
Pain intensity and frequency (Pain flares)	4.	4-week-average episodes of pain flares (≥4 on 0-10 NPRS)	11.	KOOS-child question P1 on 'Pain' subscale (1-5 Likert scale)
	5.	Worst pain past week (0-10 NPRS)	12.	Level of pain/discomfort (EQ-D5-Y 4)
Participation in sports and physical activity	6.	4-week average hours of sports participation	13. 14. 15. 16. 17.	4-week average hours of MVPA Satisfaction with extent of sports participation Pre knee pain level of sports participation Pre knee pain level of physical activity Time to return to sport (week no.)
Osgood-Schlatter morphology (ultrasound imaging)	7.	Flaviis composite severity score	18. 19. 20.	Tendinosis signs (thickening or hyperemia) Infrapatellar bursitis signs (effusion or hyperemia Hyperemia of the tibial tubercle ad modum Öhberg
Pain during knee loading	8.	Anterior Knee Pain Provocation test (0-10 NPRS)	
 
21.
 
22.
 
23.
 
24.
 
25.
 
	Pain during knee extension test (0-10 NPRS) Pressure-pain threshold at the tibial tubercle (kPa) KOOS-child 'Pain' 0-100 subscale (8 items) Known pain during manual palpation Pain during countermovement jump (0-10 NPRS)
Objective knee function			26. 27. 28. 29.	Maximal isometric knee extension strength (Nm/kg) Countermovement jump height (cm) Countermovement power (W) Knee extensor flexibility change (°)
Global rating of change	9.	7-point Likert scale	30.	Satisfaction with treatment (Y/N)
Usual activities	10.	Patient-specific function scale (NRS 0-10)	31.	Problems with usual activities (EQ-D5-Y 3)
Pain beliefs			32.	Kinesiophobia (Tampa Scale of Kinesiophobia, 17 items)
Health			33.	Self-rated health (EQ-D5-Y 0-100 VAS)
		Safety outcomes		
	1.	Any adverse events		

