#### Secondary and exploratory outcomes

#### Patient Acceptable Symptom State

The question pertaining to Patient Acceptable Symptom State (PASS) is designed in collaboration with patient representatives. The recall period will be one week, and the outlook period a 'few months' as in previous applications in musculoskeletal conditions with fluctuating symptoms. The phrasing of the PASS will be (approximate English translation): "If you consider your knee pain during the past week, and how it affects your ability to do activities of daily living (for example participating in school, in sports, and socially), would you consider your current symptom state acceptable for the next few months?". The proportions of yes/no in each group will be captured and compared at designated time points.

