#### Morphology

Involvement of the tendon is common in patients with Osgood-Schlatter, and associated signs of bursitis and severity have shown to be prognostic of a worse outcome. A series of Osgood-Schlatter patients has been described for whom less hyperemia on color doppler ultrasound was associated with milder symptoms. Hyperemia on color doppler ultrasound (ad modum modified Öhberg 1-4) will therefore be assessed for the patella tendon and tibial tubercle (yes/no) at baseline, month 3, month 5, and month 8. High inter-rater reliability of color doppler evaluations in the patella tendon has been established,, and we

are currently investigating the reliability and clinical relevance of the full ultrasound protocol being employed in the study.

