#### Global rating of change

To assess patient-assessed improvement or worsening, we will ask participants to rate their perceived level of change from their first visit on a 7-point Likert scale ranging from 'Much worse' to 'Much better'. GROC-scales have been found to have sufficient reproducibility and responsiveness.

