## Assignment of interventions: allocation

## Sequence generation {16a}

Participants will be allocated to either standardized usual care or the experimental intervention with a 1:1 allocation ratio. To perform adequate sequence generation, we will use The Robust Randomization App (RRApp v3.0.1, https://clinicalresearch-apps.shinyapps.io/rrapp/) for a computer-generate sequence in random sized blocks with no stratifications, extracted by a person not otherwise involved in the trial.

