# Data collection and management

## Plans for assessment and collection of outcomes {18a}

Depending on the time point, participants will answer between 85 (baseline) and 38 questions (month 1) in their surveys. In table 11 we have described the schedule of data collection of all outcomes. All outcome data, both clinically obtained by an outcome assessor or patient-reported directly from the participants, will be entered into REDCap. Weekly monitoring will be performed using text-based service (SMS-track®, Esbjerg, Denmark) similarly starting the following Monday after the baseline visit and the following 22 weeks, totaling 23 weekly monitoring questionnaires containing 4-6 questions.

Study phase	Pre-allocation	Baseline	Intervention period				Primary endpoint	Clinical follow-up	Long-term follow-up d
Timepoint		Mo 0	Weekly	Mo 1	Mo 2	Mo 3	Mo 5	Mo 8	Mo 10, 12, 24 48
Enrollment procedures					 	 		•	•
Clinical visit		Х		Х		Х	Х	Х	
At home	Х		Х		Х				Х
Phone screening	Х								
Written information	Х	Х							
Verbal information	X	Х							
Written consent		Х							
Allocation		Х							
Clinical assessments	1								
Clinical examination		Х					Х		
Peak Height Velocity		Х				Х	Х	Х	
Adverse events		Х		Х	Х	Х	Х	Х	
Previous & concomitant treatments		Х		Х	х	Х	Х	Х	
Clinical tests							-		
Pressure-Pain threshold		Х		Х		Х	Х	Х	
Knee extension strength		Х		Х		Х	Х	Х	
Countermovement jump		Х		Х		Х	Х	Х	
Modified Thomas test		Х		Х		Х	Х	Х	
Anterior knee pain provocation test		Х		Х		Х	Х	Х	
Objective longitudinal measures	-ii								
Physical activity (sensors)		•							
Imaging	1								
Ultrasound scanning		Х				Х	Х	Х	
Patient-reported questionnaires									
KOOS-child 4 subscales		Х		Х	х	Х	Х	х	Х
Acceptable Symptom State (PASS)		Х		Х	х	Х	Х	Х	Х
Global rating of change				Х	х	Х	Х	Х	Х
Sport & Physical activity		Х	Х	Х	х	Х	Х	Х	Х
Pain history		Х	Х	Х	х	Х	Х	Х	Х
Self-rated health (EQ-5D-Y)		Х				х	Х	Х	Х
Kinesiophobia (Tampa)		Х				Х	Х		
Therapeutic Alliance (WIA)						х			
Miscellaneous health a		Х							
Pubertal stage (Tanner)		Х				х	Х		
Adherence to treatments			Х	х		х	Х	Х	
Intervention									
Experimental or usual care treatment		—							
Complete self-management		•				.			

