## Statistical methods

## Statistical methods for primary and secondary outcomes (20a)

Analyses will be performed by a statistician blinded to group allocation and will be performed using (R Foundation for Statistical Computing, Vienna, Austria) in the Rstudio interface (RStudio Team, Boston, USA).

Change scores for KOOS-child 'sport/play' score ( $\triangle$ KOOS) from baseline to month 5 will be calculated for all participants. We will fit a linear regression model using the 'lm' function for  $\triangle$ KOOS-child as the dependent variable and including group allocation as an independent variable. Covariates are described with their measurement, timing and justification in table 12, and will potentially be added to the model.82(p9),215 In order to not introduce unnecessary bias in the model, covariates will however only be included if doing so changes the primary estimate meaningfully, as we expect a equal distribution of these pre-specified covariates given the sample size. Significance level will not determine the inclusion of covariates. The linear model will be evaluated for linearity, multicollinearity, homogeneity of variance, distortion of outliers, homoskedasticity, correlation of variables, distribution of residuals using histograms. If these model assumptions are not met non parametric bootstrap estimation and tests will be used instead. Below we have outlined the intended steps with reproducible R code for Rstudio (version 3.6, 2021.09.0+351)

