We will employ a similar analysis strategy for other numerical outcome variables. For non-numeric variables, differences between groups will be analyzed by logistic regression models, and non-normally distributed residuals for ratio-interval scale outcomes will be compared by non parametric boot strap tests. To supply detailed trajectories and inferences of treatment response over time, we will fit mixed-effects models for the imaging outcomes (months 0, 3, 5, 8); time-to-return to sport, weekly hours of sports participation, pain-flares, and sensor-based physical activity (weeks 0 to 22); clinical outcomes (months 0, 1, 3, 5, 8); and remaining patient-reported outcomes (months 0, 1, 3, 5, 8, 12, 24, 48).

Mean and SD values will be reported if data appear approximately normally distributed. If data are nonnormally distributed, they will be presented as median and interquartile range (IQR). We will report 95% confidence intervals, exact p-values to the third decimal, and discussions of minimal detectable change (MDC) and minimal important change (MIC) when relevant/possible. Frequency data will be reported as "No. (%)".

Our standard option for all variables, is to be analyzed with the highest resolution possible, meaning no collapsing or dichotomization to retain as much information as possible in the dataset. However, some assessor-dependent scales, such as ultrasound scoring of the (non-normal maturation-related) fragmentation quality of the tibial tubercle bone, contains the potential values "none" (1), "unclear", (2), "little", or "apparent/extensive" (4). The same applies to some other ultrasound measures and clinical examination findings. Depending on the distribution of responses into these categories, we might choose to exclude data from the "unclear" category or collapse the "little" and "apparent/extensive" categories if we estimate the number of responses to be too low to make meaningful inferences.

Once the primary data have been analyzed, we will also compute and report the RCT-Fragility Index (how

many patients would need to change from success to non-success to render the potential experimental effect non-significant or equal) based on the PASS outcome for easier clinical interpretation of the robustness of results.

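### The logistic comparisons of non-numeric outcomes name no baseline term although baseline status is collected: a valid analysis that gives up precision, mainly for persistent imaging signs

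*Combined protocol and SAP*

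**What the plan says.** The section on statistical methods for primary and secondary outcomes (20a) treats the two kinds of outcome differently. For the primary outcome, change scores "from baseline to month 5 will be calculated for all participants", and other numeric outcomes follow a similar strategy, so their baseline enters the analysis. After the code example, the same section says of the others: "For non-numeric variables, differences between groups will be analyzed by logistic regression models". No covariate is named. The PASS section reads the same way: "The proportions of yes/no in each group will be captured and compared at designated time points". PASS is item 2 in Table 10, directly below the primary outcome, and the Fragility Index is also built on it.

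Baseline status exists for many of these outcomes. Table 11 marks PASS, ultrasound scanning and EQ-5D-Y at month 0. The Morphology section records hyperaemia "yes/no) at baseline, month 3, month 5, and month 8". Global rating of change is an exception: participants "rate their perceived level of change from their first visit on a 7-point Likert scale", so it has no month-0 value.

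Allocation is "in random sized blocks with no stratifications". The covariate rule in 20a concerns the primary linear model: Table 12 variables may be added, and only if they shift the primary estimate meaningfully. Table 12 includes baseline Flaviis severity and baseline KOOS-child P1. It does not include baseline PASS, tendinosis signs, bursitis signs, tibial tubercle hyperaemia or the EQ-5D-Y items. Section 20a also plans mixed-effects models that include month 0. Section 20b lists the mixed-effects and covariate-adjusted models among the sensitivity analyses.

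**The concern.** A yes/no state that was present at entry often predicts the same state at month 5. A model with group alone leaves that predictable part in the noise. The numeric outcomes recover some of it through the change score; the non-numeric outcomes, as written, do not. The information has already been collected, so the loss is avoidable.

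At stake are the width of the intervals and the power of the categorical comparisons. There is also a pre-specification gap: the text does not rule out a baseline term, so whether to add one could be settled after the data are seen, for the highest-ranked secondary outcome among others.

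**Working it through.** **The plan's own figure.** The only power calculation is for the primary outcome: difference 9, SD 16, one-sided 5%, 90% power. The normal approximation gives n = 2(1.645 + 1.282)² × 16²/9² ≈ 54.1, rounded up to 55 per group. The exact one-sided t-test gives 54.82, matching the stated 54.8. Allowing for dropout, 110/0.85 = 129.4, so 130. The plan gives no power figure, prevalence or persistence rate for any non-numeric outcome, so every such input below is an assumption.

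**PASS.** Assumed: control yes at month 5 of 40%, baseline-conditional treatment odds ratio 2.7, odds ratio of 3 or 6 linking baseline yes to follow-up yes, one-sided Wald test at 5%, 2,000 simulated trials per row, 55 per arm.

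| Baseline yes | Baseline–follow-up OR | Power, group only | Power, with baseline PASS | Change (points) |
|---|---|---|---|---|
| 5% | 3 | 81.8% | 81.1% | −0.7 |
| 5% | 6 | 81.7% | 82.0% | +0.3 |
| 15% | 3 | 81.6% | 81.6% | 0.0 |
| 15% | 6 | 77.8% | 79.6% | +1.8 |
| 30% | 3 | 76.6% | 78.3% | +1.7 |
| 30% | 6 | 73.9% | 77.4% | +3.5 |
| 50% | 3 | 78.8% | 81.2% | +2.4 |
| 50% | 6 | 70.9% | 76.9% | +6.0 |

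With all 65 per arm retained, the gain runs from 0.4 to 6.7 points (0.4 to 2.8 when baseline yes is 5 to 15%). The low rows are the likelier ones. Eligibility requires markedly reduced sport or being severely affected by pain, so few participants should call their state acceptable at entry.

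**Persistent signs.** Assumed: baseline prevalence 30 to 50%, persistence 70 to 80%, new onset 10 to 15%, baseline-conditional treatment odds ratio one third, 55 per arm, one-sided 5%, 1,500 trials per scenario. These rates imply a strong baseline–follow-up association: from (0.70/0.30)/(0.15/0.85) ≈ 13 to (0.80/0.20)/(0.10/0.90) = 36. Power without and with baseline status in four scenarios was 55 and 68%, 40 and 56%, 63 and 76%, and 47 and 66%: gains of 13, 16, 13 and 19 points. A repeat with 3,000 trials per scenario gave gains of 11 to 19 points, and only 2 to 3 points when baseline prevalence was lowered to 10%.

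**Validity.** With no true effect, the PASS simulations rejected in 3.7 to 5.2% of trials unadjusted and 4.0 to 5.8% adjusted. The persistent-sign simulations rejected in 4.5 to 5.9% and 4.2 to 5.6%. All are compatible with 5%.

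**Size of a chance imbalance.** For baseline proportion q and 55 per arm, a 1.96-SD imbalance is 1.96 × √(2q(1 − q)/55): 8.1 points at q = 5% and 17.1 points at q = 30%. Multiplying by the risk difference between those yes and no at baseline (0.267 at q = 5% with odds ratio 3; 0.42 at q = 30% with odds ratio 6) moves the month-5 difference by 2.2 to 7.2 points. The unadjusted interval already allows for this movement; adjustment would remove it.

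**The case against.** The strongest reply is that an unadjusted logistic comparison of a randomised binary secondary outcome is sound. That stands. Because allocation is unstratified, a reader might infer that baseline imbalance will be mistaken for a treatment effect. The documents do not support that: randomisation keeps the test at its nominal level, stratified or not. In the persistent-sign simulations under the null, the 13 to 15% of trials that began with Arm A at least 10 points lower had false-positive rates of 21 to 30% unadjusted and 3 to 9% adjusted. Those trials were selected for imbalance in one direction. With the imbalance reversed, the unadjusted rate was 0 to 0.5%, and over all trials it was about 5%.

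A reader might also infer that PASS loses 13 to 19 points of power. That range belongs to strongly persistent signs that are common at entry. Neither the persistence nor the prevalence is documented, and the entry criteria point the other way for PASS. Pain on palpation is similarly restricted, since tenderness is one of two alternative findings in a diagnostic criterion.

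Third, the plan is silent on covariates here; it does not exclude them. Table 12 already lists the baselines of the lead ultrasound outcome (Flaviis) and of KOOS-child P1, and the mixed-effects models use month 0. This narrows the gap but does not close it. The Table 12 rule is conditional and refers to the primary estimate, the other baselines are absent, and section 20b places the models that would use baseline among the sensitivity analyses.

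**Conclusion.** The point holds as a matter of efficiency and pre-specification. The month-5 logistic comparisons name no baseline term, while the baseline status of PASS, the ultrasound signs and the EQ-5D-Y items is collected. The cost is avoidable variance, with no systematic bias. At 55 per arm the gain from adjustment is about 12 to 19 points of power for persistent signs at 30 to 50% baseline prevalence. For PASS it is about 0 to 2 points at 5 to 15% baseline yes, rising to about 6 to 7 points at 50% with a strong association, where the upper value is for 65 per arm. These sizes rest wholly on assumed prevalence, persistence and effect. The case for acting is therefore stronger for imaging signs than for PASS. This is a cheap improvement, and nothing in the primary analysis or the sample size depends on it.

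**What to change.** Add to section 20a: in each logistic model for an outcome also measured at month 0 (PASS, the ultrasound signs and stages, KOOS-child P1, the EQ-5D-Y items), that outcome's own baseline status is a fixed covariate, whatever the change-in-estimate rule gives. It is omitted where baseline has no or almost no variation, or where no baseline exists, as for global rating of change. State that this model gives the month-5 result, with the mixed-effects model as the sensitivity analysis.

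Report a standardised risk difference, averaged over the observed baseline distribution, beside the odds ratio. This meets the one small drawback: the adjusted odds ratio is conditional on baseline and differs from the crude one even when the arms are balanced.

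The cost is one SAP sentence and one model term per outcome, with no new data. The Trial status section reports recruitment complete, so the change should be dated before the analyst is unblinded.

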### Superiority framework and controlling error rates

The analysis will be evaluated based on a one-sided hypothesis as the trial employs a superiority design, meaning that if a one-sided test of significance fails in the direction of the experimental group, the null-hypothesis is rejected for our sample, and the level of significance in opposite direction is therefore not of interest. To further safeguard this choice, we have made the decision to obtain 90% power (up to 94.6% if all participants retained), corresponding to a 10% false negative error rate). By default, we will not perform adjustments for multiple comparisons as we have arranged our hypotheses in a prioritized order, and we will also conduct and report hypotheses testing in this pre-specified order. We will however adjust for multiple comparisons using Bonferroni corrections when multiple tests are performed for outcomes within the same construct or objective (e.g. the effect of group on acute pain response during loading, measured through 2 different outcomes: pain [0-10 NPRS] during maximal isometric knee extension test, and pain [0-10 NPRS] evoked from the Anterior Knee Pain Provocation test).

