# Secondary aims

- Compare secondary and exploratory patient-reported, clinical and objective measures of improvement and adverse effect, also at secondary timepoints at 3 months, and at long-term followup after 8, 10, 12, 24, and 48 months (table 10 & 11).
- Supply detailed trajectories of treatment response by collecting weekly self-reported measures and data from activity sensors during the entire 5 month core study period using visualizations and mixed effect analysis models.
- Explore factors associated with effect moderation or mediation to determine who will potentially benefit more or less of treatment, and the pontential mechanisms responsible.
- Investigate the experience of undergoing the intervention and identify potential barriers or facilitators to treatment and adherence.
- Evaluate features and procedures of the trial in a pilot-setting to assess operational feasibility

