#### Outcomes {12}

Besides long-term digital follow-up, patient-reported and clinical measures will be recorded at 5 possible time points; at baseline and months 1, 3, 5, and 8. Weekly monitoring will be done from baseline to month 5. Imaging will be performed at enrollment and at months 3, 5, and 8. Long-term patient-reported follow-up is planned for 1, 2, and 4 years after enrollment. All data, besides text-message, ultrasound images, and sensor-data, will be captured in REDCap (Research Electronic Data Capture, Vanderbilt Universit,y, USA), a logged secure system designed to capture sensitive non-commercial clinical data hosted at Hvidovre Hospital. REDCap contains options for valid values, range checks, data validation, branching, scheduling, and stop-rules to increase data quality. Pain during all clinical tests will be recorded in addition to the primary measure. Ultrasound will be performed during the enrollment visits and again at months 3, 5, and 8. For a visual overview of data collection schedule, see table 11. We have reported our outcomes in a prioritized order in addition to designations as primary, secondary or exploratory, which also reflects the order of hypothesis-testing, analyses, and intentional order of reporting, with all primary and secondary outcomes intended for the primary report. Note that for this reason, the order and count of outcomes below reflect the total number of variables of interest within each outcome. No core outcome set exists for this or similar populations, and the outcomes are chosen based on current literature and clinical experience.

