#### KOOS-child Quality of Life', 'Symptoms' and 'Pain' subscales

The above subscales will be collected and change scores compared in the same manner as the primary 'Sport/play' subscale.

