## Sample size considerations {14}

The properties of the primary outcome measure KOOS-child and the "Sport/rec" subscale have been well investigated, with a validation study including adolescent participants with Osgood-Schlatter amongst other overuse- and acute knee disorders. A small cohort of patients in our clinic (n=16) who 1) were eligible for inclusion in the trial at baseline, 2) received the intervention in question and 3) attended follow-up, reported their global rating of improvement on a 7 point Likert scale ranging from 'much worse (7)' to 'much better (1)'. Patients who reported 'much better (1)' or 'better (2)' had a mean improvement on KOOS-child

'Sport/play' subscale of 12.7±16 points, whereas patients reporting less improvement ('little' improvement or 'no change') only had a 3.57 point increase. In absence of more robust specific data in terms of severity, intervention, and length of follow-up, we will utilize this 9 point difference as a threshold for determining superiority. We consider this to be a meaningful change and a relevant between-group difference, and is within the recommended range of 8-10 points (heartbeat-med.com/resources/knee-injury-and- osteoarthritis-outcome-score-koos). This change also exceeds the smallest detectable group-level change (2.66 points) and the standard error of measurement (8.02 points).

In order to detect such a change with a standard deviation of 16 points an  $\alpha$  level (type I/false positive error rate) of 5% and power ( $\beta$ -1, or probability of avoiding type II/false negative error rate) of 90%, 55 (54.8) participants per group would be needed based on an independent one-sided t-test (R 4.0.2, Foundation for Statistical Computing, Vienna, Austria; RStudio 1.0.153, power.t.test package). To account for a potential 15% dropout rate a total of 130 participants will be included.

This will correspond to a 0.56 Cohens d 'medium' effect size at 90% power (figure 3). The smallest effect size reliably detectable will thus be >0.482 (Cohens d 'small' effect size) at  $\geq$ 80% power (Jamovi 1.2.25, jpower module), surpassing the trivial (<0.2) and small (>0.2) effect size thresholds. We also consider this sample size to be operationally feasible within the given timeframe and with the resources available to our group.

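### The prioritized order is given as the reason for no multiplicity adjustment, but without a stopping rule it gives the secondary outcomes no family-wise error control

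*Combined protocol and SAP*

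**What the plan says.** The section on the superiority framework and error rates sets the default: "By default, we will not perform adjustments for multiple comparisons as we have arranged our hypotheses in a prioritized order". It adds only that tests will be carried out and reported in that order. The next sentence makes an exception: Bonferroni correction for several outcomes within one construct or objective. It gives one example, a pair of pain-on-loading measures, and no list of groupings.

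The Outcomes section describes the Table 10 order as one "which also reflects the order of hypothesis-testing, analyses, and intentional order of reporting, with all primary and secondary outcomes intended for the primary report". Table 10 numbers 33 outcomes. It ranks outcomes, not time points.

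The Secondary aims plan comparisons "also at secondary timepoints at 3 months, and at long-term followup after 8, 10, 12, 24, and 48 months". The KOOS-child Symptoms subscale has no number in Table 10, although its section says: "The above subscales will be collected and change scores compared in the same manner as the primary".

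The significance level appears in the sample size section, for the primary outcome: "level (type I/false positive error rate) of 5% and power". Testing is one-sided: "The analysis will be evaluated based on a one-sided hypothesis as the trial employs a superiority design". The dissemination section bases the main conclusion on the between-group difference at the primary endpoint.

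**The concern.** A pre-specified order protects the error rate only when each test depends on success in all the earlier ones. The plan has the order but not the dependence. Where the authors want a condition they write one: the mediation analysis is to be done only if arm A shows a superior response. No such condition is attached to outcomes 2 to 10.

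As written, a non-significant primary result could be followed by a significant PASS or quality-of-life result in the same report, defended by pointing to the hierarchy. That is the situation a hierarchy is meant to rule out. Secondary significance is also likely to be used: Table 1 frames these outcomes as evidence of relative efficacy, exact p-values will be given, and a Fragility Index is planned on PASS, which ranks second.

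**Working it through.** **Where the 5% is spent.** The plan states no family-wise rate. Its only figure built on the 5% is the sample size. With a difference of 9, SD 16, one-sided 5% and 90% power, the normal approximation gives n = 2 × (1.645 + 1.282)² × (16/9)² ≈ 54.1 per group. The exact t-test gives 54.8, as the plan states, so 55. Then 110 / 0.85 = 129.4, rounded up to 130. The figure reproduces, and it shows that the 5% belongs to the single primary test.

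**Inputs for the family.**
- Level and direction: one-sided 5% per test, from the sections cited above.
- Number of tests: ten, reading Table 10 numbers 1 to 10 as primary plus secondary. The table as extracted shows no exploratory heading, so this is a reading.
- Correlation ρ between test statistics: not in the documents. It is assumed equal for all pairs and shown from 0 to 0.8.
- All null hypotheses true.

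**Formulas.** For test i at level aᵢ with critical value cᵢ = Φ⁻¹(1 − aᵢ):
- independent: 1 − ∏(1 − aᵢ);
- equicorrelated: 1 − ∫ φ(x) ∏ Φ[(cᵢ − √ρ·x)/√(1 − ρ)] dx.

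**Four readings of the Bonferroni step.**
- A. Not applied: ten tests at 0.05. Independent: 1 − 0.95¹⁰ = 0.401.
- B. Only outcomes 4 and 5 share a construct: eight at 0.05, two at 0.025.
- C. Applied over each full Table 10 domain. Outcomes 1, 2 and 3 stand alone (0.05 each). Outcomes 4 and 5 are in a domain of four (0.0125 each), 6 in one of six (0.0083), 7 in one of four (0.0125), 8 in one of six (0.0083), and 9 and 10 in domains of two (0.025 each).
- D. All nine secondaries form one objective: the primary at 0.05, the others at 0.05/9 = 0.0056. Independent: 1 − 0.95 × (1 − 0.0056)⁹ ≈ 0.096.

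Chance of at least one false positive:

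| Reading | ρ = 0 | 0.3 | 0.5 | 0.7 | 0.8 |
|---|---|---|---|---|---|
| A | 40.1% | 30.7% | 24.7% | 18.5% | 15.2% |
| B | 36.9% | 28.5% | 23.0% | 17.3% | 14.3% |
| C | 22.8% | 18.6% | 15.4% | 12.1% | 10.2% |
| D | 9.6% | 8.6% | 7.5% | 6.2% | 5.6% |

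**Primary non-significant, at least one false secondary.** The primary is falsely significant 5% of the time, so this chance is the table entry minus 5 points. At ρ = 0.5 it is 19.7% under A, 10.4% under C and 2.5% under D.

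**With a stopping rule.** A false positive anywhere requires the first true null in the sequence to be rejected, so the family rate is at most 5% at any correlation. Simulation under the global null gave 5.0% at ρ = 0, 0.3, 0.5 and 0.7.

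**The case against.** The strongest reply is that the plan does adjust. The Bonferroni sentence follows directly on the quoted default and is triggered by a shared construct or objective. Table 1 places PASS, quality of life, flares, worst pain, global rating and the patient-specific scale under one secondary objective. On that reading these outcomes are not tested at the full 5%, and the excess over 5% is small (reading D). This stands as far as it goes. It narrows the size of the problem, but it does not make the order a valid reason for waiving adjustment, and every reading tried still exceeds 5%. It also leaves the no-adjustment default applying to almost nothing, which shows how much depends on groupings the plan does not list. The plan's own example names two outcomes from a Table 10 domain that holds six.

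It is also fair to say that the main conclusion rests on the primary outcome alone, and that no section promises 5% across primary and secondary outcomes. A reader might infer that the trial runs at 25% in place of a promised 5%. The documents do not support that: the 5% is set for the primary test, and the 25% needs an assumed correlation of 0.5, a family of ten and no Bonferroni at all. Nor can one say that the plan controls nothing. That is true of the order alone, not of the order together with the Bonferroni step.

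The gap over time points is limited. Table 1 fixes the compared endpoints at month 5, and other times are handled mainly by mixed-effects trajectory models. The unranked Symptoms subscale is a small omission.

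**Conclusion.** The point holds for the secondary outcomes. The order has no stopping or downgrading rule, so it gives no family-wise control and does not justify omitting adjustment. The primary test keeps its one-sided 5%.

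The size depends on the undefined Bonferroni groupings and on a correlation the documents do not give. At ρ = 0.5 the family rate for outcomes 1 to 10 is about 25% with no Bonferroni, 15% with full-domain Bonferroni and 7.5% with one secondary objective. Over ρ from 0 to 0.8 the ranges are 40% to 15%, 23% to 10%, and about 10% to 6%. These figures assume equicorrelated statistics, all nulls true, and ten outcomes in the family.

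**What to change.** In the section on error rates, choose one of two wordings.

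1. *Make the order a gate.* State that outcomes 1 to 10 of Table 10 are tested at month 5 in the listed order, each at the full level, and that significance claims stop at the first non-significant result. Later outcomes in that list, outcomes 11 to 33, KOOS-child Symptoms and all other time points are then exploratory and reported as estimates with confidence intervals. Bonferroni is then not needed within outcomes 1 to 10. The downside is that a failed PASS, a binary outcome at rank 2 for which no power is stated, makes outcomes 3 to 10 descriptive.
2. *Drop the claim.* Delete the statement that ordering replaces adjustment, and label every result except the primary outcome at month 5 as exploratory, with p-values not controlled for multiplicity.

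If the within-construct Bonferroni step is kept, list which outcomes form each group.

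Either option changes wording only. The primary test, its power and the 130 participants are unaffected. Recruitment is reported as complete (130 of 130), so the choice should be fixed and dated before the allocation is unblinded.
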